--	---

	
• 5 mg → resume 5 mg• 10 mg → 5 mg• 15 mg → 10 mg 
Participants on 5 mg who have been temporarily discontinued on treatment based on clinical evaluation can be considered for dose reintroduction at 5 mg following agreement between the Investigator and the MyoKardia Medical Monitor.
 
If LVEF, plasma drug concentration, and/or QTcF persist out of range at the follow-up visit, then the participant will be discontinued from the study.
 
Participants who prematurely discontinue from the PIONEER-OLE study may be considered for rescreening for participation.
 
After Week 6, additional study visits will occur at Week 8 (\pm 7 days), Week 12 (\pm 7 days), and every 12 weeks (\pm 7 days) thereafter. Participants also will be contacted by phone in between clinic visits, at Week 18 and every 12 weeks thereafter. An end of study (EOS) visit will occur 8 weeks (\pm 7 days) after the last administration of study drug. Visits (including the Screening visit which serves as the baseline) will entail recording vital signs, targeted physical examination, ECGs, safety laboratory tests, N-terminal pro B-type natriuretic peptide (NT-proBNP), adverse events (AEs), New York Heart Association (NYHA) functional class, Kansas City Cardiomyopathy Questionnaire (KCCQ) score, and concomitant medications. Predose blood samples for assessment of drug concentration will be obtained at the time points indicated in the Schedule of Assessments. A standard TTE (including but not limited to assessment of LVOT gradient at rest and after Valsalva) will be performed at baseline and at the time points indicated in the Schedule of Assessments. In addition, a stress echocardiogram (with assessment of LVOT gradient post-exercise) will also be performed at baseline and at the time points indicated in the Schedule of Assessments.
 
For females of childbearing potential, pregnancy testing will be performed in clinic or at home every 4 weeks.
 
Participants will be followed through completion of EOS procedures. All AEs, including serious adverse events (SAEs), will be collected from the time of informed consent through the duration of the study, up to and including the Week 260/EOS visit. If there is a significant clinical abnormality or clinically significant laboratory abnormality in need of monitoring, the participant will be followed until resolution of the abnormality or until it is considered stable in the opinion of the Investigator.
 
End of Study (Week 260)
 
Participants who prematurely discontinue the study will attend an early termination visit and return to the study site 8 weeks later for an EOS visit.
 
Participants who complete 252 weeks of mavacamten treatment and do not rollover onto commercially available mavacamten will attend an end of treatment visit and return to the study site 8 weeks later for an EOS visit.

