Dose Reduction Rule: The dose may be reduced or discontinued in the case of an exaggerated pharmacologic effect at any time during the study based on the clinical judgment of the Investigator.

If results as reported by the central laboratories from any visit show mavacamten plasma concentration is ≥ 1000 ng/mL, or LVEF $< 50\%$ (as read by site), or Fridericia-corrected QT interval (QTcF) meets the following criteria, the participant will be notified by the study site/Investigator with further instructions:

- If QRS is narrow (< 120 milliseconds), then temporary discontinuation criteria are the smaller of: 15% increase from baseline QTcF OR QTcF ≥ 520 milliseconds
- If QRS is wide (≥ 120 milliseconds), then temporary discontinuation criteria are the smaller of: a 15% increase from baseline QTcF OR QTcF ≥ 550 milliseconds

Dosing with study drug will be immediately stopped and the following procedures implemented:

- If the participant is taking 5, 10, or 15 mg, study drug will be temporarily discontinued and he or she will return for an unscheduled visit (with electrocardiogram [ECG] and TTE assessments) 2 to 4 weeks later
- If LVEF $\geq 55\%$ (as read by site) and QTcF < 500 milliseconds at the unscheduled visit, then the study drug will be restarted at a lower dose, as shown below (previous dose \rightarrow restart dose):
 - 5 mg \rightarrow resume 5 mg
 - 10 mg \rightarrow 5 mg
 - 15 mg \rightarrow 10 mg

Participants on 5 mg who have been temporarily discontinued on treatment based on clinical evaluation can be considered for dose reintroduction at 5 mg following agreement between the Investigator and the MyoKardia Medical Monitor.

If LVEF (as read by site), plasma drug concentration, and/or QTcF persist out of range at the follow-up visit, then the participant will be discontinued from the study.

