For participants who do not withdraw consent for ongoing study participation but fail to return to the site, the Investigator should make every effort to contact the participant (eg, contacting participant's family or private physician, reviewing available registries or health care databases) and to determine the participant's health status, particularly vital status. Attempts to contact such participants must be documented in the participant's records (eg, number of attempts and dates of attempted telephone contact and receipt for sending a registered letter).

Participants who have withdrawn from the study cannot be treated further in the study. Their study identification numbers must not be reused.

Treatment Discontinuation

The Investigator should discontinue a participant's study treatment permanently for any of the following reasons:

- Pregnancy

- Heart failure related to systolic dysfunction
- Study termination
- Study site termination by MyoKardia (eg, in the case of major, noncorrectable protocol deviations)
- Undergoing septal reduction therapy
- Participant withdrawal from treatment or withdrawal from study

Study treatment will be discontinued in the case of exaggerated pharmacologic effect (systolic dysfunction), higher than expected plasma concentration, or excessive QT prolongation (see [Section 7.5](#)).

In addition, study treatment may be temporarily discontinued in the case of an AE or SAE at the Investigator's discretion if there is a safety concern.

In all cases, the reason(s) for permanent treatment discontinuation or study withdrawal will be recorded in the source document and on the appropriate eCRF.

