7.4.3. Criteria for Rechallenge of Mavacamten After Potential Hepatotoxicity

The decision to rechallenge the participant should be discussed and unanimously agreed upon by the Investigator and Sponsor.

If signs or symptoms recur with rechallenge, then mavacamten will be permanently discontinued. Participants who clearly meet the criteria for permanent discontinuation (as described in [Section 7.4.1](#)) should never be rechallenged.

7.5. Guidelines for the Management of Exaggerated Pharmacologic Effect (Systolic Dysfunction), Excessive QT Prolongation, or Higher Than Expected Plasma Concentration

If results, as reported by the central laboratories from any visit, show mavacamten plasma concentration is ≥ 1000 ng/mL, or LVEF $< 50\%$ (as read by site), or QTcF meets the following criteria, the participant will be notified by the study site/Investigator for further instructions.

- If QRS is narrow (< 120 milliseconds), then temporary discontinuation criteria are the smaller of: 15% increase from baseline QTcF OR QTcF ≥ 520 milliseconds.
- If QRS is wide (≥ 120 milliseconds), then temporary discontinuation criteria are the smaller of: a 15% increase from baseline QTcF OR QTcF ≥ 550 milliseconds.

It will be communicated to the Investigator and Sponsor that a stopping criterion has been met and the procedures outlined in [Section 4](#) will be implemented. If a participant discontinues study drug permanently, the participant will be encouraged to undergo ET and EOS assessments.

Any participant who experiences heart failure related to systolic dysfunction will be managed as per site-specific standard of care.

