9.5. Study Procedures by Visit

Study procedures are presented by visit in [Table 2](#) and [Table 3](#). Every effort should be made to avoid protocol deviations.

At the Investigator's discretion, unscheduled visits may be conducted for the assessment of AEs, physical examinations, vital signs, laboratory tests, drug dispensing, ECGs, and/or TTEs. All information collected from unscheduled visits will be recorded on the eCRF and included in the clinical database.

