APPENDIX 1. LABORATORY ASSESSMENTS

The following safety laboratory parameters will be measured by the central laboratory:

Hematology/Coagulation	Serum Chemistry
• CBC, including differential count	• Sodium
• Platelet count	• Potassium
• INR	• Chloride
• aPTT	• Bicarbonate
	• Calcium
	• Magnesium
	• BUN
	• Creatinine
	• ALP
	• ALT
	• AST
	• Total bilirubin
	• CPK ^a
	• Glucose
	• Protein
	• Albumin

Abbreviations: ALT, alanine aminotransferase; ALP, alkaline phosphatase; aPTT, activated partial thromboplastin time; AST, aspartate aminotransferase; BUN, blood urea nitrogen; CBC, complete blood count; CPK, creatine phosphokinase; INR, international normalized ratio.

^a If CPK is high, troponin I will be performed and reported.

At the Investigator’s discretion, safety laboratory assessments may be repeated on Day 1 to confirm study eligibility before dosing of study medication.

The following non-safety laboratory parameters will be measured at Screening:

- Hepatitis panel (hepatitis B virus and hepatitis C virus)
- Human immunodeficiency virus test
- Follicle-stimulating hormone

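### After a dosing hold, Section 4 can both restart and discontinue the same participant: the restart test omits plasma concentration and the participant's own QTcF limit, and no order of precedence is stated

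*Combined protocol and SAP*

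**What the plan says.** The Dose Reduction Rule in Section 4 has three hold triggers: plasma concentration of 1000 ng/mL or more, site-read LVEF below 50%, and a QTcF criterion. The QTcF criterion is the smaller of a 15% rise from baseline and an absolute value, which is 520 ms for narrow QRS and 550 ms for wide QRS.

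Once dosing is stopped, "he or she will return for an unscheduled visit (with electrocardiogram [ECG] and TTE assessments) 2 to 4 weeks later". If LVEF is at least 55% and QTcF is below 500 "milliseconds at the unscheduled visit, then the study drug will be restarted at a lower dose", on a schedule of 15 to 10 mg, 10 to 5 mg, and 5 mg resumed at 5 mg. The next paragraph describes reintroduction at 5 mg as something that can be considered once the Investigator and the Medical Monitor agree. The rule closes by providing that if site-read LVEF, "plasma drug concentration, and/or QTcF persist out of range at the follow-up visit, then the participant will be discontinued from the study".

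The Synopsis has the same rules in nearly the same words, including "If LVEF, plasma drug concentration, and/or QTcF persist out of range at the follow-up visit, then the participant will be discontinued from the study".

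Two other sections bear on the point. Section 5.5.1 says: "Study treatment will be discontinued in the case of exaggerated pharmacologic effect (systolic dysfunction), higher than expected plasma concentration, or excessive QT prolongation", and refers to Section 7.5. Section 7.5 repeats the triggers and, with the words "It will be communicated to the Investigator and Sponsor that a stopping criterion has been met and the procedures outlined in", sends the reader back to Section 4. Neither adds a restart condition or says which sentence of Section 4 prevails.

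**The concern.** The value that caused the hold should be part of the test that ends it. Here a hold can be caused by concentration alone, yet the restart test looks only at LVEF and QTcF. The QTcF part of that test is a flat 500 ms, while the hold criterion is relative to the participant's own baseline. The closing sentence covers concentration and QTcF, but it is not written as an exception to the restart sentence, and both are mandatory in form.

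Two sites could therefore handle the same results differently. One would restart at the listed dose; the other would discontinue the participant from the study. In a study whose primary objective is long-term safety and tolerability, that affects participant protection directly. It also affects who stays in follow-up.

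A related gap is that the sentence describing the return visit names ECG and TTE but no PK sample, although the closing rule needs a concentration at that visit.

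**Working it through.** **Rule check.** The plan has no figure of its own to reproduce here. It does not define out of range for the closing sentence, so I read it as still meeting the hold criterion. The possible states at the return visit are:

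| State | Restart sentence | Discontinuation sentence | Result |
|---|---|---|---|
| LVEF ≥ 55%, QTcF < 500 ms and below own limit, level < 1000 ng/mL | met | not met | restart |
| LVEF ≥ 55%, QTcF < 500 ms, level still ≥ 1000 ng/mL | met | met | conflict |
| LVEF ≥ 55%, level < 1000 ng/mL, QTcF < 500 ms but still ≥ 15% above baseline | met | met | conflict |
| LVEF < 50% | not met | met | discontinue |

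LVEF alone cannot produce a conflict, because ≥ 55% and < 50% exclude each other.

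**QTcF overlap.** The hold limit is the smaller of 1.15 × baseline and 520 ms (or 550 ms). It lies below the 500 ms restart limit when 1.15 × baseline < 500, that is, when baseline < 500 / 1.15 = 434.8, or about 435 ms. Example: with a baseline of 420 ms the hold limit is 1.15 × 420 = 483 ms. A return value of 490 ms passes the restart test and still meets the hold criterion. The documents give no distribution of baseline QTcF, so the frequency cannot be computed.

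**Concentration overlap.** The documents give no half-life figure; the amendment summary only calls the terminal half-life long. I assume first-order decline off drug with a half-life h of 7, 14 or 28 days.

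- Level at the hold needed to be at 1000 ng/mL after d days: 1000 × 2^(d/h).
- Level after d days from a hold at exactly 1000 ng/mL: 1000 × 2^(−d/h).

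| Return visit | Half-life | Level needed at hold (ng/mL) | Ratio to 500 ng/mL (top of target range) | Level after a hold at exactly 1000 (ng/mL) |
|---|---|---|---|---|
| 14 days | 7 days | 4000 | 8.0 | 250 |
| 14 days | 14 days | 2000 | 4.0 | 500 |
| 14 days | 28 days | 1414 | 2.8 | 707 |
| 28 days | 7 days | 16000 | 32 | 63 |
| 28 days | 14 days | 4000 | 8.0 | 250 |
| 28 days | 28 days | 2000 | 4.0 | 500 |

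A participant would need to be well above the hold limit when stopped to be still above it on return.

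**Is a level taken at the return visit?** The Section 4 sentence names ECG and TTE. Section 9.5 says "unscheduled visits may be conducted for the assessment of AEs, physical examinations, vital signs, laboratory tests, drug dispensing, ECGs, and/or TTEs". The list in Appendix 1, introduced by "The following safety laboratory parameters will be measured by the central laboratory", does not include mavacamten concentration. By contrast, the liver-injury work-up in Appendix 3 names PK sampling expressly. Table 2, footnote a, refers to Table 3 for unscheduled visits, and the Table 3 grid is not readable in the text available. This leaves the question open.

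**The case against.** The strongest reply is that this is one procedure, read in order. The restart bullet gives the ordinary path, and the closing sentence removes anyone still out of range. Section 5.5.1 points the same way. I accept that this is probably the intent, but the reader has to infer it, because no sentence makes the second rule an exception to the first.

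A reader might infer that drug is restarted without the level being checked. The documents do not support that. The closing sentence presupposes a concentration at the follow-up visit, the Table 3 grid may list one, and Section 9 lets the Investigator add unscheduled safety assessments. The absence of mavacamten from Appendix 1 is weak evidence, since that is a safety laboratory list and PK has its own row in Table 2. What stands is narrower: the sentence describing the visit does not name the sample that the closing rule needs.

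Two mandatory rules is also too strong a description at 5 mg, where agreement with the Medical Monitor is mentioned. That matters, because everyone starts at 5 mg and 6 of the 20 Target Doses in Table 1 are 5 mg. It adds a third statement, however, and does not settle which rule prevails.

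There is other partial cover. Restart from 10 or 15 mg is at a lower dose, the Investigator may reduce or stop the drug at any time for an exaggerated effect, and a resting TTE follows about 28 days after a dose adjustment. That TTE visit comes after restart.

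Finally, the concentration conflict should be rare, and enrolment is at most 20. This limits the size of the point. It does not remove the QTcF overlap.

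**Conclusion.** The point holds as a conflict between two safety rules with no stated precedence, in Section 4 and in the Synopsis. It arises in two states: acceptable LVEF and QTcF with a level still at or above 1000 ng/mL, and QTcF below 500 ms but still at least 15% above a baseline below about 435 ms. It does not show that the plan intends dosing at a high level, or that no level is measured before restart.

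The rarity of the concentration conflict rests on the assumed first-order decline and the 7-to-28-day half-life range; its actual frequency, like that of the QTcF overlap, cannot be computed from the documents. Both conflicts depend on reading out of range as still meeting the hold criterion. This is a minor to moderate correction that should be made.

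**What to change.** Make three changes, in Section 4 and in the Synopsis:

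1. Describe the return visit as including ECG, TTE and, after a concentration-triggered hold, a PK sample.
2. Make restart require LVEF of at least 55%; QTcF below 500 ms and below the participant's own hold criterion; and, after a concentration-triggered hold, plasma concentration below 1000 ng/mL.
3. State that the discontinuation rule prevails over the restart rule when any measure still meets its hold criterion.

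The cost is one PK tube per concentration-triggered hold, at a visit already required, plus wording in two places. The downside is a short wait for the assay before restart. Table 2, footnote a, does make resumption wait for notification by the site, but it is tied to the missed-visit procedure in Appendix 4 and should not be relied on to cover this wait. On the reading of out of range used here, change 3 adds no discontinuations beyond those the present closing sentence already requires. If Table 3 already lists PK at unscheduled visits, change 1 only restates it; changes 2 and 3 are still needed.

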4.1. Study Duration

The expected study duration is approximately 264 weeks: up to 4 weeks for Screening, a 252-week (5-year) treatment period, and an 8-week posttreatment follow-up period, or until mavacamten becomes commercially available. If mavacamten clinical development is discontinued, this study will be terminated. The EOS is defined as the date of the last observation of the last participant.

Table 2 Schedule of Assessments – Screening Through Year 2

Assessment ^a	Year 1												Year 2									
	Screening Days -28 to -1	Day 1	Wk 4	Wk 6	Wk 8	Wk 12	Wk 18	Wk 24	Wk 30	Wk 36	Wk 42	Wk 48	Wk 54	Wk 60	Wk 66	Wk 72	Wk 78	Wk 84	Wk 90	Wk 96	Wk 102	
Telehealth Visit ^b							X		X		X		X		X		X		X		X	
Informed consent	X																					
Medical history ^c	X																					
Vital signs ^d	X	X	X	X	X	X		X		X		X		X		X		X		X		
AEs/SAE ^e	X	X	X	X	X	X	X	X	X	X	X	X	X	X	X	X	X	X	X	X	X	
Concomitant therapy	X	X	X	X	X	X	X	X	X	X	X	X	X	X	X	X	X	X	X	X	X	
Physical examination ^f	X	X	X		X	X		X		X		X		X		X		X		X		
ECG ^g	X	X	X		X	X		X		X		X		X		X		X		X		
Resting TTE ^h	X		X		X	X		X		X		X				X				X		
Stress TTE ^h	X		X									X				X						
Mavacamten 5 mg daily		←→																				
Dosing		←→																				
Dose adjustment up to target ⁱ			←→																			
IMP compliance check ^j			X	X	X	X		X		X		X		X		X		X		X		
Hepatitis panel and HIV test	X																					
PK sample ^k			X		X			X		X		X		X		X				X		
Chemistry	X		X			X				X				X		X				X		
Hematology	X		X			X				X				X		X				X		
NT-proBNP ^l	X	X	X		X	X		X		X		X		X		X				X		
FSH ^m	X																					
Pregnancy test (β-hCG) ⁿ	X	X	X		X	X	X	X	X	X	X	X	X	X	X	X	X	X	X	X	X	
NYHA class, KCCQ	X	X	X		X			X				X				X				X		

Abbreviations: β-hCG, beta-human chorionic gonadotropin; AE, adverse event; BP, blood pressure; ECG, electrocardiogram; eCRF, electronic case report form; FSH, follicle-stimulating hormone; HCM, hypertrophic cardiomyopathy; HIV, human immunodeficiency virus; IMP, investigational medical product; KCCQ, Kansas City Cardiomyopathy Questionnaire; LVOT, left ventricular outflow tract; NT-proBNP, N-terminal pro B-type natriuretic peptide; NYHA, New York Heart Association; PK, pharmacokinetic(s); SAE, serious adverse event; TTE, transthoracic echocardiography; Wk, week.

Note: The Week 4 visit has a visit window of ± 4 days; all remaining visits have a window of ± 7 days.

Table 2 Schedule of Assessments – Screening Through Year 2 (Continued)

- ^a At the Investigator's discretion, unscheduled visits may be conducted at the investigational site for the assessment of AEs, physical examinations, vital signs, laboratory tests, drug dispensing, ECGs, and/or TTEs (see [Table 3](#)). Unscheduled safety assessments will be conducted for participants who temporarily discontinue study drug prior to resuming dosing, as outlined in [Appendix 4](#). Study drug will be dispensed at the unscheduled visit; however, participants will not resume dosing until notified by the study site. All information collected from unscheduled visits will be recorded on the eCRF and included in the clinical database.
- ^b Assessments as part of telehealth visits are to be conducted via telephone or other technology based on standard at institution.
- ^c A complete medical history will be recorded at the Screening visit, which will include evaluation (past or present) of the following: general, head and neck, eyes, ears, nose, throat, chest/respiratory, heart/cardiovascular, gastrointestinal/liver, gynecological/urogenital, musculoskeletal/extremities, skin, neurological/psychiatric, endocrine/metabolic, hematologic/lymphatic, allergies/drug sensitivities, past surgeries, substance abuse, or any other diseases or disorders as well as participation in clinical studies (study medication and/or device or other therapy). Specific history related to a participant's HCM diagnosis will also be collected.
- ^d Vital signs will be taken in the sitting position prior to dosing and will include heart rate and BP after resting for at least 5 minutes. BP should be taken via an automated recorder. Respiratory rate will be obtained at Screening after resting for at least 5 minutes. Temperature will be obtained at Day 1.
- ^e Any changes in baseline conditions that occur after the informed consent form is signed, but prior to the first dose of IMP, are recorded on the medical history eCRF, unless the change is related to a study procedure, in which case it is considered an AE. All changes that occur after administration of the first dose of IMP and meet the definition of an AE are recorded as AEs.
- ^f At Screening, a complete physical examination will be conducted, including a neurological examination (gross motor and deep tendon reflexes), height and weight, and assessment of the following: general appearance, skin, head and neck, mouth, lymph nodes, thyroid, abdomen, musculoskeletal, cardiovascular, neurological, and respiratory systems. At all other onsite visits, an abbreviated cardiopulmonary physical examination will be conducted, with other systems assessed as directed by interval history; weight will also be recorded at all physical examinations.
- ^g A 12-lead ECG will be performed after 10 minutes of rest. On Day 1, ECG will be performed predose.
- ^h Instantaneous peak LVOT gradient (baseline) and provoked peak LVOT gradient (Valsalva maneuver) will be assessed. Ejection fraction (2-dimensional), left ventricular fractional shortening, global longitudinal strain by speckle tracking, and velocity timing interval will be analyzed. Resting TTE should be performed prior to stress echocardiography. All stress echocardiograms should include a 4-hour fast prior to exercise. If the post-exercise LVOT gradient is measured ≥ 50 mmHg, further dose adjustment may be considered and discussed with the MyoKardia Medical Monitor. If dose adjustment occurs at Week 24 or beyond, a follow-up visit (to mirror Week 8 assessments) should be scheduled 4 weeks later (± 7 days) to include a TTE assessment. All stress echocardiography visits will be conducted in the clinic.
- ⁱ Dose adjustment is optional. Dose adjustments beyond the Target Dose may only be exceeded for each given participant following discussion between the Investigator and the MyoKardia Medical Monitor. Lower doses are permissible.
- ^j Compliance with study drug will be monitored by capsule count at each clinic visit.
- ^k A blood sample will be collected prior to dosing for assessment of trough study drug plasma concentrations. On days of visits, participants should not take their daily dose prior to visit. Study drug will be administered on site to facilitate collection of this sample.
- ^l The blood draw for NT-proBNP will occur prior to stress echocardiography.
- ^m FSH testing at Screening for postmenopausal females to confirm postmenopausal status.
- ⁿ Pregnancy test (serum or urine) for females of childbearing potential, based on standard at institution. A urine pregnancy test is performed at home every 4 weeks when no clinic visit is scheduled.

Table 3 Schedule of Assessments – Year 3 Through End of Study (Continued)

- ^c Participants who complete 252 weeks of mavacamten treatment and do not rollover onto commercially available mavacamten will attend an EOT visit and return to the study site 8 weeks later for an EOS visit. Participants who rollover onto commercially available mavacamten at any time will be contacted 8 weeks later by telephone or other technology for an EOS follow-up to assess AEs, concomitant medications, and pregnancy.
- ^d At the Investigator's discretion, unscheduled visits may be conducted at the investigational site for the assessment of AEs, physical examinations, vital signs, laboratory tests, drug dispensing, ECGs, and/or TTEs. Unscheduled safety assessments will be conducted for participants who temporarily discontinue study drug prior to resuming dosing, as outlined in [Appendix 4](#). Study drug will be dispensed at the unscheduled visit; however, participants will not resume dosing until notified by the study site. All information collected from unscheduled visits will be recorded on the eCRF and included in the clinical database.
- ^e Assessments as part of telehealth visits are to be conducted via telephone or other technology based on standard at institution.
- ^f Vital signs will be taken in the sitting position prior to dosing and will include heart rate and BP after resting for at least 5 minutes. BP should be taken via an automated recorder. Respiratory rate will be obtained at the Week 260/EOS visit after resting for at least 5 minutes. Temperature will be obtained at the Week 260/EOS visit.
- ^g Any changes in baseline conditions that occur after the informed consent form is signed, but prior to the first dose of study medication, are recorded on the medical history eCRF, unless the change is related to a study procedure, in which case it is considered an AE. All changes that occur after administration of the first dose of study medication and meet the definition of an AE are recorded as AEs.
- ^h At the visits indicated, an abbreviated cardiopulmonary physical examination will be conducted, with other systems assessed as directed by interval history; weight will also be recorded at all physical examinations.
- ⁱ A 12-lead ECG will be performed after 10 minutes of rest.
- ^j Instantaneous peak LVOT gradient (baseline) and provoked peak LVOT gradient (Valsalva maneuver) will be assessed. Ejection fraction (2-dimensional), left ventricular fractional shortening, global longitudinal strain by speckle tracking, and velocity timing interval will be analyzed. Resting TTE should be performed prior to stress echocardiography. All stress echocardiograms should include a 4-hour fast prior to exercise. If the post-exercise LVOT gradient is measured ≥ 50 mmHg, further dose adjustment may be considered and discussed with the MyoKardia Medical Monitor. If dose adjustment occurs after Week 24, a follow-up visit (to mirror Week 8 ([Table 2](#)) assessments) should be scheduled 4 weeks later (± 7 days) to include a TTE assessment. All stress echocardiography visits will be conducted in the clinic.
- ^k Dose adjustment is optional. Dose adjustments beyond the Target Dose may only be exceeded for each given participant following discussion between the Investigator and the MyoKardia Medical Monitor. Lower doses are permissible.
- ^l Compliance with study drug will be monitored by capsule count at each clinic visit.
- ^m A blood sample will be collected prior to dosing for assessment of trough study drug plasma concentrations. Study drug should be administered on site to facilitate collection of this sample.
- ⁿ The blood draw for NT-proBNP will occur prior to stress echocardiography.
- ^o Pregnancy test (serum or urine) for females of childbearing potential, based on standard at institution. A urine pregnancy test is performed at home every 4 weeks when no clinic visit is scheduled.

